## **4. SELECTION AND ENROLLMENT OF PARTICIPANTS**

### **4.1 Inclusion Criteria**

LEOs will be recruited from PPB, APD, and MPD. We will over recruit for a target final sample across sites of 20% women and 35% racial/ethnic minorities.

Eligible participants must: 1) be 21-65 years old (age limitations for both police departments); 2) demonstrate English fluency; 3) be a sworn LEO at the rank of Sergeant or below; 4) agree to random assignment to condition; and 5) be willing to complete assessments at multiple time points and participate in intervention groups.

### **4.2 Exclusion Criteria**

Individuals will be excluded from participation if they: 1) have participated in MBSR, MBRT or a similar mindfulness course, 2) score in the severe range on brief screening measures of depression, suicidal ideation, alcohol use, or PTSD, or 3) are unable or unwilling to give written informed consent.

### **4.3 Study Enrollment Procedures**

*Recruitment.* LEOs will be recruited from PPB, APD, and MPD. PPB employs 966 full-time, active duty officers, serving approximately 603,106 citizens in the Greater Portland Metropolitan Area; women and racial/ethnic minorities represent 16% and 16%, respectively. APD employs 921 full-time, active duty officers, serving approximately 907,301 citizens in the Greater Albuquerque Metropolitan Area; women and racial/ethnic minorities represent 16% and 47%, respectively. MPD employs 486 full-time, active duty officers, serving approximately 258,054 citizens in the Greater Madison Metropolitan Area; women and racial/ethnic minorities represent 28% and 21%, respectively. We will over recruit for a target final sample across sites of 20% women and 35% racial/ethnic minorities (see Inclusion Enrollment Report).

In collaboration with human resources staff at PPB, APD, and MPD, we will recruit 104 LEOs for study participation, conducted via: 1) emailed invitations sent to all eligible LEOs, 2) informational website and flyers posted at PPB, APD, and MPD facilities, and 3) community-based police organization leadership. We used similar recruitment methods for our R21 study and met recruitment goals. Co-I's [name], [name], and [name] will oversee recruitment at PPB, APD, and MPD, respectively. Recruitment will include information about interventions, assessed outcomes, concordance between community and investigator goals, and research team contact information. Interested individuals will voluntarily contact the research team by phone for eligibility screening. They will be informed of study purpose, eligibility criteria and randomization process. If the officers are interested in participation and believe the study may be

a good fit for them, they will provide informed consent via REDCap, then screen for eligibility criteria. Eligible LEOs will be mailed a dried blood spot collection kit immediately after the consenting process, and will make a remote (via Zoom) appointment for baseline assessment.

*Screening Log.* Interested individuals will be tracked using REDCap. Data collected will include reasons for ineligibility and for non-participation of eligible candidates.

*Informed Consent.* Study staff will obtain informed consent via REDCap from all participants prior to screening and baseline data collection. The consent form will include information about randomization, release of information (including data from PPB and APD databases), researchers' responsibilities regarding records collected, DHHS certificate of confidentiality, registration with clinicaltrials.gov, and permission to audio and video record sessions.

*Randomization.* Study staff not involved in data collection will randomly assign participants to condition using SPSS and REDCap, stratifying for gender, using a permuted-block randomization procedure frequently used in MT trials to ensure balance within strata and across groups. The study statistician will create an allocation table using SPSS, and upload it to REDCap, which will be used to implement the randomization procedure.

Following completion of the baseline online survey and confirmed completion of the dried blood spot sample, participants will be assigned using a 2:1.5:1 ratio (MBRT = 47; SME = 35; NIC = 22), allowing more robust evaluation of measure sensitivity and responsiveness as well as more accurate parameter estimation for the MBRT group. **Randomization will occur separately at each site to ensure equal ratios at all sites across the three arms.**

Participants will be notified of group assignment via phone call by a study team member. Participants assigned to MBRT and SME conditions will receive emailed information regarding course structure, dates/times, and class format. All participants will be provided information on assessment timeline, reminder calls they will receive, and contact information for the research team. Participants assigned to SME or NIC will be offered an opportunity to attend an MBRT course after the final 12-month follow-up collection of departmental excessive use of force data.

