#### **2: Ensure fidelity and equivalence of lab, assessment, and data management procedures across sites**

- 2.1 Assess and improve efficiency of data collection and procedures for on-the-job LEO excessive use of force (e.g., aggressive drawing and discharge of weapons, vehicle rams, and illegal takedowns)
- 2.2 Confirm acceptability of self-report (resilience, aggression, burnout, depression, suicidal ideation, trauma, and alcohol misuse) and stress-related proinflammatory biomarkers (C-reactive protein [C-RP], interleukin 6 [IL-6], interleukin 10 [IL-10], tumor necrosis factor-alpha [TNF- $\alpha$ ]) data collection
- 2.3 Train relevant study staff in REDCap and confirm compliance with Good Clinical Practice procedures

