## **1. STUDY OBJECTIVES**

### **1.1 Primary Objective**

#### **Objective 1: Enhance efficiency of recruitment, engagement, and retention across sites.**

We will successfully enroll 52 LEOs at Albuquerque, 26 at Portland, and 26 at Madison, with an *across-site average* of 20% female and 35% racial/ethnic minority participants; 85% of participants will attend  $\geq$  6 MBRT or SME sessions (i.e., treatment completer), and complete 75% of assigned homework. Based on 80% retention at *3 months* in the recent R21, enhanced retention efforts will result in  $\geq$  80% at *6 months*.

Per NCCIH SARP guidelines, we will gauge accrual and retention by accrual of  $\geq$  80% but no higher than 150% of benchmark number at a given time point, study initiation delay of  $\leq$  1 accrual reporting period ( $\sim$ 4 months), and actual loss to follow-up rate  $\leq$  20%.

**Objective 2: Ensure fidelity and equivalence of lab, assessment, and data management procedures across sites.** 100% of staff will complete trainings in research ethics, an NIH Good Lab Practice course, and all assessment and lab procedures. Throughout the study, there will be  $\leq$  5% rate data procedural errors, tracked in REDCap (same procedure used in R21 study). Based on the R21 study, we expect  $\leq$  15% missing data due to omitted or refused completion of measures from active participants. Collection of self-report measures will be acceptable to LEOs at all sites, i.e., all assessments will be completed in the allotted time, assessment burden will be acceptable, and questionnaire items will be relevant and acceptable ( $\geq$  75% of LEOs rate assessment protocol as “reasonable” or “very reasonable” in content, clarity and time burden). We will obtain departmental excessive use of force (i.e., BlueTeam or other departmental data) for 100% of participants at all sites in designated period (1 month to assemble pre-baseline, and 1 month to assemble at 12-month follow-up). Biweekly reviews will yield 100% adherence to data management protocol at both data collection sites.

**Objective 3: Optimize intervention training procedures and ensure fidelity to intervention protocols across sites.** All study MBRT and SME interventionists will complete intensive clinical trainings, demonstrate 90% fidelity on Adherence and Competence scales, and

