### **Randomization**

Immediately following completion of the Zoom-facilitated baseline assessment session, and confirmed completion of the dried blood spot sample, study staff not involved in data collection will randomly assign participants to condition using SPSS and REDCap. The study statistician will create an allocation table using SPSS, and upload it to REDCap, which will be used to implement the randomization procedure for all sites. All trial randomization codes will be stored within REDCap, which is a secure (HIPAA-compliant) internet-based survey and data management software system housed on a secure server at Oregon Health and Science University.

Participants will then be notified via phone of group assignment by a study team member. Participants assigned to MBRT and SME conditions will receive emailed information regarding course structure, dates/times, and class format. All participants will be provided information on assessment timeline, reminder calls they will receive, and contact information for the research team. Initiation of study intervention will be between 1 and 21 days. Participants assigned to SME or NIC will be offered an opportunity to participate in an MBRT course after the final 12-month follow-up collection of departmental excessive use of force data. Participants in all conditions will have access to resources provided by PPB, APD or MPD, including counseling services.

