#### **6.2.4 Followup Visits**

Postcourse followup (must occur within 21 days of end of 8-week intervention period).

- Proinflammatory Cytokines (C-RP, IL-6, IL-10, TNF- $\alpha$ )
  - Dried Blood Spot Collection Kit
- Psychological Resilience
  - Brief Resilience Scale
- Alcohol Misuse
  - PROMIS Alcohol Use
  - PROMIS Alcohol Use Negative Consequences
- Depression
  - PROMIS Depression
- Sleep Disturbance
  - PROMIS Sleep Disturbance
- Mindfulness
  - Five Facet Mindfulness Questionnaire – Short Form
- Self-Compassion
  - Self-Compassion Scale – Short Form
- Aggression
  - Buss Perry Aggression Questionnaire – Short Form
- Suicidal Ideation
  - Concise Health Risk Tracking - Self-Report
- Trauma Symptoms
  - PTSD Checklist for DSM-5
- Burnout
  - Oldenburg Burnout Inventory
- Sustained Attention to Response Task
- Interoceptive Awareness
  - Multidimensional Assessment of Interoceptive Awareness-II
- Perceived Stress
  - Perceived Stress Scale-10
- Global Impression of Change

- Acceptability
  - Acceptability of Assessment Procedures
  - Postcourse Satisfaction Survey (MBRT and SME)
- Intervention Compliance
  - Meditation Practice Questionnaire (MBRT)
  - Ilumivu (MBRT and SME)

3- and 6-month follow-up (must occur within  $\pm 10$  days of target date. Target date is relative to end of the intervention period, i.e., 90 days for 3-month followup, and 180 days for 6-month followup):

*Note: 6-month follow-up is final study visit.*

- Proinflammatory Cytokines (C-RP, IL-6, IL-10, TNF- $\alpha$ ) (**Only at 3-month follow-up**)
  - Dried Blood Spot Collection Kit
- Psychological Resilience
  - Brief Resilience Scale
- Alcohol Misuse
  - PROMIS Alcohol Use
  - PROMIS Alcohol Use Negative Consequences
- Depression
  - PROMIS Depression
- Sleep Disturbance
  - PROMIS Sleep Disturbance
- Mindfulness
  - Five Facet Mindfulness Questionnaire – Short Form
- Self-Compassion
  - Self-Compassion Scale – Short Form
- Aggression
  - Buss Perry Aggression Questionnaire – Short Form
- Suicidal Ideation
  - Concise Health Risk Tracking - Self-Report
- Trauma Symptoms
  - PTSD Checklist for DSM-5
- Burnout
  - Oldenburg Burnout Inventory

- Sustained Attention to Response Task
- Interoceptive Awareness
  - Multidimensional Assessment of Interoceptive Awareness-II
- Perceived Stress
  - Perceived Stress Scale-10
- Intervention Compliance
  - Meditation Practice Questionnaire (MBRT)
  - Ilumivu (MBRT and SME)

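### Biomarker acceptability (aim 2.2) is measured only after a randomization step that requires a completed blood spot, so officers who decline or fail the first kit are in none of the ratings

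*Combined protocol and SAP*

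**What the plan says.** - **Order of events.** Section 4.3 states that "Eligible LEOs will be mailed a dried blood spot collection kit immediately after the consenting process". Section 6.2.2 dates enrollment at signature of the consent form. Assignment follows the baseline survey and "confirmed completion of the dried blood spot sample, participants will be assigned using a 2:1.5:1 ratio". The Randomization paragraph of section 6.2.2 repeats the condition: "Immediately following completion of the Zoom-facilitated baseline assessment session, and confirmed completion of the dried blood spot sample".
- **Aim.** Item 2.2 of the Précis is to confirm the acceptability of collecting self-report data and "stress-related proinflammatory biomarkers" (C-RP, IL-6, IL-10, TNF-α).
- **Targets.** Section 1.1, Objective 2, expects at most 15% "missing data due to omitted or refused completion of measures from active participants". It also says that "Collection of self-report measures will be acceptable to LEOs at all sites", judged by whether at least "75% of LEOs rate assessment protocol as" reasonable or better. Neither target names the blood spot.
- **When acceptability is measured.** "Acceptability of Assessment Procedures" is listed in section 6.2.4 at the postcourse visit, and the schedule in section 6.1 shows it at Visit 2 only. The interview question on blood spot burden (section 9.6, Qualitative) is asked after the post-intervention assessment.
- **Screening log.** Section 4.3 provides a REDCap log that holds the reasons why eligible candidates do not take part. No target in section 1.1 and no analysis in section 9.6 refers to it.

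**The concern.** The plainest sign that home blood collection is unacceptable is an officer who will not do it the first time. Under the plan that officer can be eligible, consented, enrolled and mailed a kit, yet is never randomized and so is never asked for a rating or an interview. What remains is acceptability among people who have already done the procedure once.

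The trial exists to choose measures and procedures for a later efficacy trial. If loss at the first kit goes unreported, the later trial could keep the blood spot, and possibly the same randomization condition, without an estimate of what that step costs in recruited officers.

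**Working it through.** **Nothing to reproduce.** The 15% and 75% figures are stated targets without a derivation. The only computed figure nearby is the arm split, which is not at issue.

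**Step 1: who can be counted where.**

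| Officer | Screening log | Post-visit rating | Interview | 15% target |
|---|---|---|---|---|
| Randomized | not applicable | yes, if attending | yes, if taking part | yes, while active |
| Consented and mailed a kit, no baseline sample | plausibly, with a reason | no | no | unclear: active is not defined |

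**Step 2: baseline samples.** If all 104 are randomized under this rule, refused or omitted baseline samples among them are 0 of 104, whatever the true refusal rate. Confirmed completion does not guarantee an assayable sample, so assay failures are a separate matter.

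**Step 3: effect on a pooled 15% target.** The documents do not say how the target is pooled. Suppose it is applied to the three scheduled samples per officer (baseline, post-intervention, 3 months):
- Samples: 3 × 104 = 312. Allowed missing: 0.15 × 312 = 46.8.
- None of the refused or omitted samples can fall at baseline, so all fall among 2 × 104 = 208 follow-up samples: 46.8 / 208 = 22.5%.

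Follow-up missingness could then reach 22.5% and the pooled target would still be met.

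**Step 4: sensitivity to refusal at the kit.** Let r be the share of officers who refuse, among those who either refuse or are randomized. Logistical and sampling failures are left out. The documents give no value, so r from 0% to 25% is an assumption.
- Officers in the denominator: 104 / (1 − r), rounded up.
- A measured 15% missing becomes 1 − (1 − r) × 0.85, with a refuser counted as missing throughout.
- A measured 75% acceptability becomes 0.75 × (1 − r), with a refuser counted as non-accepting.
- Measured acceptability needed for 75% overall: 0.75 / (1 − r).

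| r (assumed) | Denominator | Baseline sample refused | 15% becomes | 75% becomes | Needed for 75% |
|---|---|---|---|---|---|
| 0% | 104 | 0/104 = 0% | 15.0% | 75.0% | 75.0% |
| 5% | 110 | 6/110 = 5.5% | 19.3% | 71.3% | 78.9% |
| 10% | 116 | 12/116 = 10.3% | 23.5% | 67.5% | 83.3% |
| 15% | 123 | 19/123 = 15.4% | 27.8% | 63.8% | 88.2% |
| 20% | 130 | 26/130 = 20.0% | 32.0% | 60.0% | 93.8% |
| 25% | 139 | 35/139 = 25.2% | 36.3% | 56.3% | 100% |

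The acceptability columns also assume that randomized officers who miss the post visit would have rated like those who attend. Section 9.2 predicts 20% overall attrition, so the raters will probably be fewer than 104.

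**The case against.** The case on the other side has real substance.

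- **No biomarker target exists.** A reader might infer that the trial could pass a biomarker benchmark only because refusers were filtered out. The documents do not support that. The 75% sentence opens with self-report measures, the 15% target covers measures in general, and aim 2.2 sets no threshold for the blood spot. This stands: the bias bears on what aim 2.2 can conclude, not on a numeric pass mark for biomarkers.
- **Refusers need not be invisible.** The screening log can hold their reasons, and consent-dated enrollment supplies a denominator. This stands, and it is why the remedy is cheap. But the plan does not commit to using either for this purpose.
- **The term active participant is undefined.** A reader might infer that refusers are certainly outside the 15% target. Because enrollment precedes the kit, a reading that includes them is possible. It is an ambiguity.
- **Inclusion criterion 5 requires willingness to complete assessments.** Willingness stated at screening is not completion of a kit that arrives later. Treating non-completers as ineligible would hide the refusals rather than measure them.
- **Follow-up samples still test the procedure.** True for two of the three collections, but only among officers who completed the first.
- **Not every missing kit is a refusal.** Postal delay, scheduling or a failed finger-stick is not non-acceptance. This stands, so only refusals belong in the sensitivity figure.
- **If the efficacy trial keeps the same condition, missingness among randomized officers is the right planning figure for its biomarker analysis.** This also stands. Loss at the kit is then a matter of recruitment yield, but recruitment barriers are themselves an objective (item 1.4), and the documents do not say whether the condition will be kept.

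**Conclusion.** The point holds as a selection problem in how a stated objective is measured. Two sections make the completed blood spot a condition of randomization, and every planned acceptability measure comes later. Aim 2.2 is therefore tested, for the biomarkers, only in officers who have already accepted the procedure once, with zero refused or omitted baseline samples by construction.

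Its size is unknown. The table is a range under an assumed refusal rate, and at r = 0 nothing changes. A reader might infer from it that the targets would be missed; nothing in the documents supports a particular r. Nor does the point mean that baseline biomarker data will be complete, since assay failures remain possible.

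The revision history says the blood spot was added in Version 12. If the first cohort was randomized before then, fewer than 104 officers passed through this step and the counts above shrink; the reasoning is the same for those who did.

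This is a cheap and worthwhile improvement to reporting, not a flaw in the randomization.

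**What to change.** 1. As the biomarker acceptability result for aim 2.2, report baseline kit completion among all eligible consented officers mailed a kit, by site. Take the reasons from the screening log and separate refusal from logistical or sampling failure.
2. State that active participants in the 15% target means randomized officers.
3. Show the 15% and 75% targets for randomized officers. Beside each, give a sensitivity figure that counts kit refusals, but not all non-completers, as missing or non-accepting.
4. Keep the randomization condition as it is.

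**Cost.** The screening log and consent dates are already planned. The documents do not say whether kit mailings are recorded or whether the log's reasons distinguish refusal from failure; if not, one or two REDCap fields are needed. No new assessment is added. The downside is that the reported figures may be less favourable.

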## 5. STUDY INTERVENTIONS

### 5.1 Interventions, Administration, and Duration

Both MBRT and SME will include psychoeducation, gentle movement exercises focused on stress reduction and fitness, and weekly homework assignments, and will be matched for time and assigned homework.

MBRT will be delivered in groups of 10 to 13 law enforcement officers, in 8 weekly sessions of 1 hour each, with the exception of weeks 1 and 7 which are extended 7- and 4-hour classes, respectively, for a total of 17 intervention hours. The extended session, modeled after MBSR, is intended to provide an immersive training experience. The session will contain a series of mindfulness practices, including body scan, mindful movement, and walking and breath-focused

meditations. The session will focus primarily on formal mindfulness practices, in contrast to inclusion of discussion and psychoeducational components contained in other MBRT sessions.

If state, local and university allow Sessions 1 and 7 to be in-person, they will be conducted at the study sites. If not, they will be conducted using the online Zoom platform. Any MBRT in-person intervention sessions will be held in reserved rooms able to accommodate up to 25 people, and large enough to comply with social distancing guidelines - specifically, the Psychology Research Lab in Portland, and at UNM Department of Psychology in Albuquerque. All MPD groups will be conducted remotely. Online groups will be facilitated via Zoom. MPI [name] and Co-Is [name] and [name] will oversee MBRT interventionist training. [name] co-developed MBRT, and is an expert in MBIs with first responders; [name] and [name] have facilitated, trained and supervised MBIs, and have collaborated on multiple MBI-related NIH trials.

SME will be delivered as a weekly, 8-week, 1.5 hour class, except for weeks 1 and 7 which are extended to 4-hour classes, for a total of 17 intervention hours, with weekly homework (amount matched to MBRT), and gentle movement exercises. The content focuses on psychological, physiological, and dietary effects of stress, time management techniques, fitness, sleep hygiene, nutrition, and factors mitigating effects of stress. [name] (SME developer) will provide input and support to ensure interventionists are trained to fidelity. Training will be conducted by trainers approved by [name], with experience conducting SME and training interventionists. MPI [name], a licensed clinical psychologist with experience facilitating stress management groups, will oversee SME training with support from [name]. Potential adverse effects include: minor aches or strains from mindful movement practices, and mild emotional distress completing self-report measures or exposure to the socially evaluative cold pressor task challenge procedures.

MBRT and SME groups will be led by separate interventionists, with at least masters level training in mental health or a related field, and matched for level of education and experience. MBRT interventionists will have previous training in and experience with MBRT or related interventions (e.g., MBSR, MBCT or MBRP), and will undergo intensive training, weekly clinical supervision, and regular meetings with MPIs to discuss fidelity and other clinical issues. Drs. [name], [name], and [name] are clinical psychologists with combined knowledge of psychoeducational protocols, MBIs, first responder populations, trauma, substance abuse, and other psychosocial outcomes. They each have extensive experience developing, implementing, supervising, and assessing similar interventions.

Given the importance of internal validity of interventions in RCT research, careful attention will be given to intervention adherence and consistency across sites, with all sessions audio and video recorded. Under supervision of Drs. [name], [name], [name] and consultant [name], advanced graduate students at both study sites will review four randomly selected sessions from each MBRT and SME cohort, adapting the MBRP Adherence and Competence measure used in previous trials. Drs. [name], [name] and [name] will provide weekly supervision to all interventionists to ensure fidelity and minimize drift.

Participants randomized to the NIC condition will not receive any intervention, but will participate in the same assessments as the two active intervention conditions (i.e., at baseline, post-intervention, 3- and 6-month follow-up). Assessment times will be yoked to those of the two active intervention conditions.

